5.2.3 Steroids

Corticosteroids should be used at the lowest dose to control symptoms of edema and mass effect, and discontinued, if possible. Use of corticosteroids should be recorded in the PBTC Rave database.

5.2.4 Anticonvulsants

Anticonvulsants drugs should be used, if indicated. Use of anticonvulsants should be recorded in the PBTC Rave database. Note: Use of valproic acid or enzyme inducing anti-convulsants is prohibited on this trial. Note that levetiracetam (Keppra) may cause prolongation of the QTc and patients who must remain on Keppra should be closely monitored.

5.2.5 Growth Factors

Routine use of growth factors (i.e. G-CSF, GM-CSF and erythropoietin) is not permitted. However, therapeutic use of G-CSF or GM-CSF in patients with serious neutropenic conditions, such as sepsis, may be considered at the investigator's discretion. Use of growth factors should be recorded in the PBTC Rave database.

5.2.6 Anti-emetics

The use of anti-emetics will be at the investigator's discretion. Use of anti-emetics should be recorded in the PBTC Rave database. Steroids should not be used as anti-emetics when possible.

5.2.7 Febrile neutropenia

Febrile neutropenia should be managed according to the local institutional guidelines. Measures

include laboratory testing, blood and urine cultures, and institution of broad spectrum antibiotics.

5.2.8 *Pneumocystis jiroveci pneumonia (PJP) prophylaxis*

The use of medication (e.g., Bactrim) for PJP prophylaxis in patients on chronic steroids is recommended but is at the investigator's discretion.

5.2.9 *Neurosurgical or other surgical procedures*

If a neurosurgical procedure or other surgical procedure is required for a reason other than tumor progression (i.e. the onset of hydrocephalus), these procedures should be documented, but will not constitute criteria for declaring the patient "off therapy". Panobinostat should be held until the patient is clinically stable and has recovered from the acute effects of surgery.

5.2.10 *Diarrhea*

Patients should be advised to drink plenty of water or rehydration fluids to avoid dehydration if diarrhea occurs. Should diarrhea occur, investigators should ensure that patients have loperamide on hand and follow the loperamide dosing guidelines in **Table 12** below, at first onset of the symptom. Dehydration prevention and correction of electrolyte disturbances should be practiced as per institution's SOP. Stool count and consistency should be noted in the patient diary if treatment for diarrhea is instituted.

Refer to **Table 13** for details of panobinostat dose reduction, and **Table 12** below for details of suggested loperamide dosing based on patients body weight.

Table 12

Weight Specific Guidelines for Therapeutic Use of Loperamide			
Weight (kg)	Initial (Loading) Loperamide dose (mg)	Subsequent daytime loperamide dose	Subsequent nighttime loperamide dose
8-10	1	0.5mg q 3h	0.75mg q 4h
10-20	1	1mg q 3h	1mg q 4h
20-30	2	1mg q 3h	2mg q 4h
30-42	2	1mg q 2h	2mg q4h
42	4	2mg q 2h	4mg q 4h

5.3 *Duration of Therapy*

In the absence of treatment delays due to adverse event(s) or disease progression, treatment may continue for 26 courses (approximately 2 years) or until one of the Off Treatment Criteria applies as noted in Section 5.3.2.

5.3.1 *On Study Data Submission Schedule*

Pre-treatment, on-study and off-treatment data, as well as patient response data are to be recorded in the electronic data collection screens using the PBTC Rave database. See the Required Data

and Timetable for Submission form located on the PBTC-047 Protocol webpage for the schedule. For assistance, contact the PBTC Protocol Coordinator listed on the cover page. An optional roadmap is located on the PBTC-047 Protocol Webpage.

5.3.2 *Off Treatment Criteria*

At the discontinuation of treatment, the “Off Treatment Date” is to be recorded in the eCRF and is to be consistent with the reason given for going off treatment. The “Last Treatment Date” is defined as the last date that the patient received protocol based therapy. Date of “off treatment” must be the greatest of the date of last treatment, date of procedure, date of patient assessment, notification of patient/family decision, or decision made by the physician that resulted in the patient being taken off protocol treatment. The reason for discontinuation of treatment must be documented by the attending investigator in the medical record and recorded in the eCRF.

Patients will be considered Off Treatment for the following reasons:

- Development of unacceptable toxicity as outlined in Section 5.1.3. See Section 7 for specific adverse event reporting requirements.
- Progressive disease (PD) as described in Section 11.2.4.
- Development of a medical or psychiatric illness or social issue that in the investigator's judgment renders the patient incapable of further therapy on this protocol or the treating physician determines continuation on this study is not in the patient's best interest.
- The patient, parent or legal guardian refuses further treatment on this protocol. In this case the investigator should clarify if the family also wishes to withdraw consent for continued participation for data collection purposes.
- Completion of all protocol defined treatment
- Pregnancy
- Non-compliance that in the opinion of the investigator does not allow for ongoing participation.

Patients who are off protocol therapy must be followed until an “Off Study Criterion” is met.

5.3.3 *Data Submission Schedule for Patients Off-Treatment*

Patients will be followed initially for the resolution of all toxicities considered at least possibly related to panobinostat occurring while on treatment and for 30 days after the last administration of study drug. Patients will continue to be followed for 3 years from the initiation of protocol treatment for the monitoring of unexpected later developing toxicities or other morbidity and to document disease progression and survival. Once patients are off-treatment and treatment-related toxicities have resolved or another treatment started, follow up during this 3-year period may be done electronically or by phone. Data should be updated quarterly in the PBTC Rave database.

5.3.4 *Criteria for Removal from Study*

The date and reason for the patient coming off study must be documented in the eCRF and the OBDMC must be notified according to standard reporting guidelines (see Sections 7 for adverse events, Section 5.3.5 for Data submission for Off Study, Section 12 for Data Reporting, and the Required Data and Timetable Submission from located on the PBTC-047 protocol webpage).

- Patient determined to be ineligible.
- Parent, patient, or guardian withdraws consent for continued participation.
- Patient death while on study. The IRB, Study Chair and OBDMC must be notified as per Section 7.3.
- Patients removed from treatment for reasons other than withdrawal of consent or Death will be followed until three years have elapsed from the date of initiation of protocol therapy on this study.

5.3.5 *Data Submission for Patients Off-Study*

No data will be collected documenting treatment or reporting events or disease status that occur subsequent to the official “off study” date, with the exception of adverse events with an attribution of possible, probable, or definite that occur after the “off study” date for agents being studied under an IND (see **Section 7**).

6 Dosing Delays/ Dose Modification

6.1 *Notification of Study Chair*

The study chair or co-chair must be notified of any dosage modifications, prior to the implementation of the dose modification

6.2 *Hematologic and Non-Hematologic Adverse Events and Management*

The criteria for dose modifications for study drug-related toxicity are detailed in **Table 13**.

Dose Modification for Hematological Toxicity

If a patient experiences dose-limiting hematological toxicity as outlined in Section 5.1.4.2 (i.e. grade 4 thrombocytopenia [$< 25 \times 10^9/L$] or grade 3 thrombocytopenia [< 50 and $\geq 25 \times 10^9/L$] with bleeding, or grade 3 twice within 1 treatment cycle or grade 4, or grade 3 or 4 febrile neutropenia) treatment will be withheld. Platelets should be transfused to a count of $> 100 \times 10^9/L$ (i.e. a post-transfusion platelet count should be obtained). Counts should then be checked every 3-4 days (and when medically indicated) during this time.

If the toxicity resolves to meet on study parameters within 14 days of drug discontinuation, provided there is no current active bleeding in the case of dose-limiting thrombocytopenia, the patient may resume therapy at one dose level lower. Patients who are dose-reduced for toxicity will not have their dose re-escalated.

If toxicity does not resolve to meet on study parameters within 14 days of drug discontinuation, the patient must be removed from protocol therapy.

Only one dose-reduction per patient is allowed. If any dose-limiting toxicity occurs in a patient already dose-reduced for toxicity, the patient must be removed from protocol therapy.

Table 13

Criteria for dosing delays, dose-reductions, and re-initiation of treatment due to study drug-related non-hematological toxicity (excluding QT prolongation)

Worst Toxicity CTCAE Grade* unless otherwise specified (Value)		Dose Modification Guidelines At any time during a course of therapy (including intended day of dosing) Note: If dose limiting toxicity does not resolve after holding drug for 14 days, patient will be removed from treatment
NON-HEMATOLOGICAL TOXICITIES		
CARDIAC		
Cardiac - Prolonged QT interval**		Please refer to Section 6.3.
GASTROINTESTINAL		
Diarrhea	Grade 2 (4-6 stools/day over baseline, etc.) despite the use of optimal antidiarrheal medications	None. If unacceptable to patient or medically concerning, then hold until recovery to \leq grade 1, or baseline, up to 14 days, then restart original schedule at unchanged dose level
	Grade 3 (\geq 7 stools/day over baseline, etc.) despite the use of optimal antidiarrheal medications	Temporarily discontinue panobinostat dosing until resolved to \leq grade 1, or baseline, then restart original schedule reduced by one dose level
	Grade 4 (life-threatening consequences, hemodynamic collapse, etc.) despite the use of optimal antidiarrheal medications	Discontinue panobinostat dosing
Vomiting/Nausea***	Grade 1, 2 not requiring treatment or controlled using standard anti-emetics	Maintain dose level
	Grade 3 that resolves to \leq grade 2 with standard emetics within 5 days	Maintain dose level
	Grade 3 or 4 vomiting or Grade 3 nausea that cannot be controlled or does not resolve to \leq grade 2 within 5 days despite the use of standard anti-emetics	Temporarily discontinue panobinostat dosing until resolved to \leq grade 1, or baseline, then restart panobinostat reduced by one dose level
FATIGUE		
Fatigue	Grade 3	Temporarily discontinue panobinostat dosing until resolved to \leq grade 2, or baseline, then: 
 • If resolved within 7 days after suspending panobinostat, then restart panobinostat at an unchanged dose level • If resolved in more than 7 days after suspending panobinostat, then restart panobinostat reduced by one dose level

Worst Toxicity CTCAE Grade* unless otherwise specified (Value)		Dose Modification Guidelines At any time during a course of therapy (including intended day of dosing) Note: If dose limiting toxicity does not resolve after holding drug for 14 days, patient will be removed from treatment
NON-HEMATOLOGICAL TOXICITIES		
	Grade 4	Temporarily discontinue panobinostat dosing until resolved to \leq grade 2, or baseline, then: 
 • restart panobinostat reduced by one dose level
HEPATIC		
Total Bilirubin	Grade 3 or 4	Temporarily discontinue panobinostat dosing until resolved to \leq grade 2, or baseline, then restart panobinostat reduced by one dose level
Note: If Grade 3 or Grade 4 hyperbilirubinemia is due to the indirect component only, and hemolysis as the etiology has been ruled out as per institutional guidelines (e.g., review of peripheral blood smear and haptoglobin determination), then reduction of one dose level and continuation of treatment is at the discretion of the Investigator.		
AST/SGOT, ALT/SGPT	$> 5-10 \times \text{ULN}$	Temporarily discontinue panobinostat dosing until resolved to \leq grade 1 or baseline, then: 
 • If resolved within 7 days, then: 
 • restart panobinostat at unchanged dose level • If resolved in more than 7 days, then reduce panobinostat by one dose level
	$> 10 \times \text{ULN}$	Temporarily discontinue panobinostat dosing until resolved to \leq grade 1, or baseline, then: 
 • restart panobinostat reduced by one dose level
All dose modifications should be based on the worst preceding toxicity.		
* Common Terminology Criteria for Adverse Events (CTCAE Version 4.0 or 5.0; see Section 7.2)		
** It is critical that electrolyte abnormalities be followed closely and corrected prior to dosing		
*** See also concomitant medication Section 5.2.		

6.3 Dose Modifications for Prolonged QTc

All cardiac events should be treated according to the local standard of care and referred to a cardiologist if clinically indicated. The localized readings of ECGs will use the Fridericia correction for QTc interval assessment: QTcF. Any final decisions concerning dose modifications or permanently discontinuing the patient from study drug due to QTcF prolongation will be based on the Investigator's clinical assessment. Any plan to deviate from these guidelines must be previously discussed and agreed upon with the PI.

Patients must have QTcF < 450 msec to be eligible for the trial. If QTcF is \geq 450 msec or above 60 msec from pre-treatment ECG, correct any electrolyte abnormalities (hypokalemia, hypomagnesemia, hypocalcemia), and conduct triplicate ECGs (5 minutes apart) and calculate average QTcF. If the average QTcF from the triplicate ECGs remains \geq 450ms, patient must not be dosed. Pre-dose ECG monitoring is mandatory on days 1 and 5 of course 1, and day 1 of courses 2 through 4. Post dose ECG (3 hours post dosing) is mandatory only on days 1 and 5 of course 1. On day 5 of course 1, ECG may be performed at a local institution but results must be faxed to treating institution within the same day.

If a pre-treatment or post-dose ECG shows a QTcF \geq 500ms, patient is not eligible for further treatment. If any of these mandatory ECGs show QTcF \geq 450 msec or 60 msec above baseline, dosing should be held and the above specified measures including follow-up triplicate ECGs and correction of electrolyte abnormalities should be performed. If QTcF abnormality resolves, patients should resume treatment and have QTcF checked pre-dose on day 1 of each course for at least the next 3 subsequent courses. Additional QTcF monitoring should be performed if clinically indicated. If a patient cannot be dosed due to prolonged QTcF for more than 7 days since last dose, patient must be discontinued from study treatment.

Table 14

Dose Reductions for QTc Prolongation

Time Point	Average QTcF*	Action
Screening	\geq 450 msec	Patient is not eligible to enroll
pre-dose course 1 day 1	\geq 470 msec	Delay treatment Correct any electrolyte abnormal values ** and repeat ECG, if the average QTcF \geq 470 msec, do not dose
	Above 500 msec	Patient is not eligible to receive any treatment
Pre-dose course 1 day 5 Pre-dose day 1 of subsequent courses	\geq 450 msec or above 60 msec from baseline for any pre-dose ECG after the patient has commenced treatment***	Omit dose If unresolved within 7 days, discontinue treatment If resolved within 7 days, resume treatment at prior dose for initial occurrence or at reduced dose if recurrent
	Above 500 msec	Permanently discontinue treatment

*QTcF: Heart rate corrected QT interval using the Fredericia formula: QTc=QT/RR0.33
**: serum potassium, magnesium, calcium,
***If a single pre-dose QTcF is \geq 450 msec or 60 msec from baseline, subsequent ECGs should be performed in triplicate

7 Adverse Events: List and Reporting Requirements

Adverse event (AE) monitoring and reporting is a routine part of every clinical trial. The following list of AEs (Section 7.2) and the characteristics of an observed AE (Section 7.2) will determine whether the event requires expedited reporting (via CTEP-AERS) **in addition** to routine reporting. The coding of attribution in the PBTC Rave database pertains to adverse events related to panobinostat.

- *Baseline Abnormalities*

Any baseline (pretreatment) abnormalities observed during the initial physical examination should be recorded in the PBTC Rave database.

- *Treatment or within 30 days of treatment*

Only record adverse events grades 1 and 2 if the attribution is at least possibly related to panobinostat. Record all adverse events grades 3 through 4 and deaths), regardless of attribution on the electronic case report forms.

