- Serum total calcium (correct for serum albumin) or ionized calcium $\geq \text{LLN}$
- Serum creatinine based on age/gender as noted in **Table 9**. Patients that do not meet the criteria in **Table 9** but have a 24-hour Creatinine Clearance or GFR (radioisotope or iothalamate) $\geq 70 \text{ ml/min}/1.73 \text{ m}^2$ are eligible.

Table 9

Serum Creatinine for age/gender		
Age	Maximum Serum Creatinine (mg/dL)	
	Male	Female
2 to < 6 years	0.8	0.8
6 to < 10 years	1	1
10 to < 13 years	1.2	1.2
13 to < 16 years	1.5	1.4
≥ 16 years	1.7	1.4

The threshold creatinine values in this Table were derived from the Schwartz formula for estimating GFR (Schwartz et al. J. Peds, 106:522, 1985) utilizing child length and stature data published by the CDC.

- Cardiac Function:
 - Left ventricular ejection fraction ≥ 50 by gated radionuclide study OR shortening fraction of $\geq 27\%$ by echocardiogram
 - Patient has no ventricular arrhythmias except for benign premature ventricular contractions.
 - Patient has a QTc interval < 450 ms.

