3.6 Criteria to Start Treatment

- Subjects must start therapy within seven (7) days of enrollment.
- Laboratory values must be no older than 7 days prior to the start of therapy. If a test that is repeated post enrollment and prior to the start of therapy is outside the limits for eligibility, it must be rechecked within 48 hours prior to the start of therapy. If rechecks are still outside the limits for eligibility, the patient may not receive protocol therapy and will be considered off study
- Cardiac requirements: please see Section 3.3.7.
- If, in the opinion of the treating physician, a patient's neurologic condition significantly worsens within 72 hours prior to treatment, the patient should not start treatment and should be taken Off Study.

4 Registration Procedures

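### Before the first dose, Table 14 withholds panobinostat only at a QTcF of 470 msec or more, where the rest of the protocol uses 450; the 7-day stopping limit also lacks a common start in the text and the table

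*Combined protocol and SAP*

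**What the plan says.** **Threshold.** The Section 6.3 text makes a pre-dose ECG mandatory on days 1 and 5 of course 1 and on day 1 of courses 2 to 4. After electrolyte correction and triplicate ECGs its rule is: "If the average QTcF from the triplicate ECGs remains \geq 450ms, patient must not be dosed". It adds: "If any of these mandatory ECGs show QTcF \geq 450 msec or 60 msec above baseline, dosing should be held". Section 3.6, on starting treatment, says "Cardiac requirements: please see Section 3.3.7", and the criterion there is "Patient has a QTc interval < 450 ms". Section 3.1.7 sets the same limit.

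Table 14 also uses 450 msec at screening and for pre-dose ECGs once treatment has begun. Its row for pre-dose course 1 day 1 differs: it delays treatment at 470 msec or more, then directs the site to "repeat ECG, if the average QTcF \geq 470 msec, do not dose". The only other entry for that time point bars treatment above 500 msec.

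**Stopping limit.** The text takes the patient off study treatment under this condition: "If a patient cannot be dosed due to prolonged QTcF for more than 7 days since last dose". Table 14, for course 1 day 5 and day 1 of later courses, says to omit the dose and then: "If unresolved within 7 days, discontinue treatment If resolved within 7 days, resume treatment at prior dose for initial occurrence". It gives no day from which the 7 days run.

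**The concern.** Table 14 is the part of Section 6.3 that a site is likely to keep at hand. Someone using it before the first dose finds nothing to do at 450 to 469 msec, while the text rules out dosing across that band. The background section on cardiac safety (within Section 2.3.3.3) records a boxed warning for severe and fatal cardiac events, and the participants are children. A dosing threshold should not depend on which part of a section the site reads.

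The stopping limit matters for a different reason. It decides whether a child whose QTcF recovers stays on treatment. If the text and the table start the count on different days, two sites could handle the same hold differently, one discontinuing and the other resuming.

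**Working it through.** The plan gives no figure to reproduce here. The check compares the provisions and counts days.

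**1. Threshold, side by side**

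| Place | Time point | Action starts at |
|---|---|---|
| 3.1.7, 3.3.7 | Eligibility | 450 msec |
| 3.6, through 3.3.7 | Start of treatment | 450 msec |
| 6.3 text | Any mandatory ECG, including pre-dose course 1 day 1 | 450 msec |
| Table 14 | Screening | 450 msec |
| Table 14 | Pre-dose course 1 day 1 | **470 msec** |
| Table 14 | Pre-dose course 1 day 5 and day 1 of later courses | 450 msec |

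The unmatched band is 470 − 450 = 20 msec, that is 450 to 469 in whole milliseconds.

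Take a child whose average is 460 msec on day 1 and does not change. The table raises no objection to the first dose, whereas the text forbids it. The text also says "Post dose ECG (3 hours post dosing) is mandatory only on days 1 and 5 of course 1", so an ECG follows 3 hours later; at 460 the text then holds dosing. If the child reaches day 5 unchanged, Table 14 itself omits that dose. The 470 row is therefore out of line with the table's own next row as well as with the text.

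**2. Days since last dose**

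Inputs are the preferred Monday/Wednesday/Friday schedule (Section 5.1), 28-day courses (Section 5.1.2) and no delay.

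- Stratum 1 doses: days 1, 3, 5, 8, 10, 12, 15, 17, 19.
- Stratum 2 doses: days 1, 3, 5, 15, 17, 19.
- Day 1 of the next course is day 29, so days since last dose = 29 − 19 = 10 in both strata.

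Ten exceeds 7. On the literal text, a hold on day 1 of courses 2 to 4 that is not cleared that day is already past the limit.

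**3. Where the limits fall**

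Table 14 states no start. The table column below assumes that its clock starts at the omitted dose.

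| Hold | Text, literal | Table 14, from omitted dose |
|---|---|---|
| Pre-dose, course 1 day 5 (last dose day 3) | 3 + 7 = day 10 | 5 + 7 = day 12 |
| Pre-dose, day 1 of courses 2 to 4 (last dose day 19) | 19 + 7 = day 26, already past | 29 + 7 = day 36 |

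Day 36 is 36 − 19 = 17 days since the last dose.

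**4. Can the two be reconciled?**

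If the text counts only days on which QTcF itself prevented dosing, its count for a day 29 hold starts on day 29 and ends on day 36. For a day 5 hold it starts on day 5 and ends on day 12. Both then match the table. This needs two things that neither place states: that the text ignores planned rest days, and that the table counts from the omitted dose.

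**The case against.** **Opposite instructions.** A reader might infer that the table tells the site to dose at 450 to 469 msec. It does not. The day 1 row says when to delay and is silent below 470. A site that obeys every provision will withhold at 450, because the text and Section 3.6 both require it. This stands: there is one out-of-line row, not two balanced rules. It does not remove the problem, because silence in an action table is easily read as no action needed.

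**Narrow exposure.** Eligibility already required a value below 450 msec, and treatment must start within 7 days of enrollment. Few children may fall in the band on day 1. This also stands, and the documents give no figure for how many would.

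**A deliberate margin.** The 470 could be an intended tolerance for ECG variation after enrollment. Nothing in the protocol says so, and Section 3.6 and the text contradict it.

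**The clock.** The text does not count bare days since the last dose; it speaks of a patient who cannot be dosed because of prolonged QTcF. In a planned rest week the schedule, not the QTcF, is why no dose is given. The same paragraph also says that patients resume once the abnormality resolves. This is a strong argument, and it is why a proven contradiction between the two limits cannot be claimed. The text still names the last dose as the start and does not exclude rest days.

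**Central oversight.** Final decisions rest on the investigator's assessment, deviations need agreement with the PI, and Section 6.1 requires the study chair to be told before a dose modification. These steps bring cases to attention but do not say which threshold or which start applies.

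**Conclusion.** The threshold point holds as written. Table 14's pre-dose course 1 day 1 row should read 450 msec, and the 20 msec gap could let a site give a first dose that the text forbids. This rests on comparing provisions and needs no assumption about event rates.

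The stopping-limit point holds as an ambiguity. On the literal text, 10 days have passed against a 7-day limit on day 1 of courses 2 to 4. On the more natural reading, rest days do not count and the text agrees with the table, provided the table's clock starts at the omitted dose. The day counts assume the Monday/Wednesday/Friday schedule with no delay.

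A reader might go further and infer that the mismatch distorts the DLT count or the MTD, or that a number of affected patients can be given. The documents do not support either. A split DLT call would need a particular hold, a narrow window of recovery dates and an assumed clock start. The adult QTcF rates quoted in the background cover any time after baseline, so they do not measure first-dose values or unresolved day 1 holds. Nor is the lack of a fixed day for repeating the ECG a conflict: the text requires follow-up triplicates, and further ECGs when clinically indicated.

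**What to change.** 1. In Table 14, pre-dose course 1 day 1, change both 470 msec entries to 450 msec, keeping the greater-than-or-equal sign.
2. In both the Section 6.3 text and Table 14, count the 7 days from the date on which QTcF first prevented dosing. For a pre-dose hold this is the date of the first withheld dose. For a hold triggered by a post-dose ECG it is the date of that ECG.

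The post-dose wording keeps the text's present limits: 1 + 7 = day 8 for the day 1 ECG and 5 + 7 = day 12 for the day 5 ECG. Counting a Stratum 2 post-dose day 5 hold from the next withheld dose would instead give 15 + 7 = day 22.

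The cost is a wording amendment and a memo to sites. The first change only tightens the table. The second loosens the literal text in two places: the pre-dose day 5 limit moves from day 10 to day 12, and the limit on day 1 of courses 2 to 4 moves from already expired to day 36, up to 17 days since the last dose. Table 14 already permits both if its clock starts at the omitted dose, but the sponsor should accept the change knowingly.

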Treatment may be administered on an outpatient basis. Reported adverse events and potential risks are described in Section 7. Appropriate dose modifications are described in Section 6. No investigational or commercial agents or therapies other than those described below may be administered with the intent to treat the patient's tumor.

5.1 *Agent Administration*

Patients with recurrent/progressive DIPG will be enrolled at the time of progression in Stratum 1. Therapy with panobinostat will be administered every other day, 3 times/ week, p.o. preferably on a Monday/Wednesday/Friday schedule for three weeks, followed by one week off of therapy. Three weeks of therapy plus the one week rest period (total 4 weeks) will constitute one course. Treatment will continue for up to 26 courses (approximately 2 years) barring progressive disease or unacceptable toxicity.

Patients with DIPG or H3K27M+ Thalamic DMG who have not progressed will be enrolled after receiving standard radiation therapy in stratum 2 and cannot begin treatment until at least 14 days after completion of radiation. Therapy with panobinostat will be administered every other day, 3 times/ week, every other week. **A minimum of 6 days without drug is required between treatment weeks.** Four weeks will constitute one course. Treatment will continue for up to 26 courses (approximately 2 years) barring progressive disease or unacceptable toxicity.

5.1.1 *Panobinostat*

Panobinostat will be provided by Secura Bio Inc. Oral panobinostat will be supplied as 5 mg, 10 mg, 15 mg orange colored, and/or 20 mg reddish colored opaque, hard gelatin capsules.

Subjects will be assigned a dose level at the time of enrollment. See Section 5.1.6 below for details of dose escalation schedule. See Section 6 for dose modifications.

Dosing should be adjusted based on BSA calculated at the beginning of each course of therapy. The dose prescribed should be rounded to the nearest deliverable dose based on the BSA adjustment and the available pill sizes. Dosing Tables which reflect this approach are available in **Appendix D: Dosing Tables**. Patients will be provided with a Medication Diary for panobinostat, instructed in its use, and asked to bring the diary as well as the remaining pill bottles with them to each appointment. The Patient Diary is available in

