Appendix E: Patient Diary.

Patients are encouraged to take their dose of panobinostat at the same time each day, preferably in the morning. Each dose of panobinostat should be taken with a 4 oz / 120 ml glass of water. Drug must be taken on an empty stomach (either 1 hour before or after meals) on Course 1, Days 1 and 3, and may be taken with or without food for the remaining doses. Patients should be instructed to swallow the capsules whole and not chew them. Patients must avoid grapefruit or grapefruit juice and Seville (sour) oranges during the entire study.

If the patient forgets to take his/her dose during the morning on a scheduled treatment day, then he/she should take panobinostat on that same day within 12 hours after the missed dose if possible. After more than 12 hours, that day's dose should be withheld, and the patient should wait to take panobinostat until the next scheduled treatment day (i.e., patients should be instructed not to try to make-up the missed dose after 12 hours). The patient should then continue treatment with the original dosing schedule. If vomiting occurs within 15 minutes, the dose should be repeated. If a dose is missed/ unable to be given, record on the patient diary and continue counting the days of the course, with treatment administered on originally scheduled days.

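### Section 6.3 and Table 14 run different 7-day clocks for prolonged QTcF, and read literally the text's clock has already expired at the day 1 ECGs of courses 2 to 4

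*Combined protocol and SAP*

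**What the plan says.** The text of Section 6.3 makes pre-dose ECGs mandatory on days 1 and 5 of course 1 and on day 1 of courses 2, 3 and 4. If one of these shows QTcF of 450 ms or more, or 60 ms above baseline, the dose is held, electrolytes are corrected and ECGs are repeated in triplicate. The paragraph lets treatment resume once the abnormality has resolved, then closes with a mandatory stop: "If a patient cannot be dosed due to prolonged QTcF for more than 7 days since last dose, patient must be discontinued". The start of that clock is named: it is the last dose.

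Table 14 covers the course 1 day 5 pre-dose ECG and "Pre-dose day 1 of subsequent courses". For QTcF of 450 ms or more, or more than 60 ms above baseline, the dose is omitted, and then: "If unresolved within 7 days, discontinue treatment". The other branch reads: "If resolved within 7 days, resume treatment at prior dose for initial occurrence or at reduced dose if recurrent". Neither branch names the day from which the 7 days run.

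The calendar comes from elsewhere. Sections 5.1 and 5.1.2 and the Appendix E diaries set a 28-day course with three doses in each treatment week: weeks 1 to 3 in Stratum 1, weeks 1 and 3 in Stratum 2. For Stratum 2, Section 5.1 adds: "A minimum of 6 days without drug is required between treatment weeks". When a dose is missed, Section 5.1.1 and the diaries tell the patient to "continue counting the days of the course, with treatment administered on originally scheduled days".

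**The concern.** Both schedules end each course with a planned drug-free stretch, and the course 2 to 4 ECGs come at the end of it. A clock that starts at the last dose has been running through that whole stretch, although nothing was wrong with the ECG. If the stretch is longer than 7 days, the text's limit is used up before the first abnormal tracing can exist.

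The text would then require permanent discontinuation of a child whom Table 14 would hold for up to 7 days and possibly resume. It would also leave no use for the resume-on-resolution step in its own paragraph. Two sites following the same section could manage the same finding differently, and the reasons recorded for leaving treatment would mix two rules.

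**Working it through.** **Check on the calendar.** Doses on days 1, 3 and 5 of each treatment week give:

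- Stratum 1: days 1, 3, 5, 8, 10, 12, 15, 17, 19, which is 9 doses.
- Stratum 2: days 1, 3, 5, 15, 17, 19, which is 6 doses.

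Section 11.1.1 uses 9 and 6 as its per-course denominators, so the calendar agrees with the plan's own figure.

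**Day 1 of courses 2, 3 and 4 (both strata).**

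- Next course starts: 28 + 1 = day 29.
- Age of the last dose at the ECG: 29 − 19 = 10 days. If the day 19 dose was missed: 29 − 17 = 12 days.
- Text limit, counted from the last dose: 19 + 7 = day 26, which is 29 − 26 = 3 days before the ECG.
- Table 14 limit, if counted from the omitted day 29 dose: 29 + 7 = day 36.
- Difference between the two clocks: 36 − 26 = 10 days.

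If Table 14 were instead counted from the last dose, it would match the text. Its resume branch could then never apply at these ECGs on the nominal calendar, because day 26 comes before day 29.

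**Course 1 day 5, pre-dose.** The last dose was day 3.

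- Text limit: 3 + 7 = day 10.
- Table 14 limit, if counted from the omitted day 5 dose: 5 + 7 = day 12.
- Difference: 2 days.

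**Sensitivity to the gap.** The Monday/Wednesday/Friday pattern is a preference, so the gap can be shorter. With only the minimum 6 drug-free days in Stratum 2, the last dose is 6 + 1 = 7 days old at the next dose, which is not more than 7. The literal clock would then still be open at the ECG but would run out the next day.

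| ECG | Last dose | Age at ECG | Text limit | Table 14 limit, from omitted dose |
|---|---|---|---|---|
| Course 1 day 5, pre-dose | day 3 | 2 days | day 10 | day 12 |
| Day 1 of courses 2–4 (day 29 of the preceding course) | day 19 | 10 days | day 26 | day 36 |

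**The case against.** The best defence is that the stop has a cause condition: the child must be undosed because of QTcF. In the rest week the child is undosed because of the schedule. If only the QTcF-caused hold counts, the clock starts at the day 1 ECG, the hold-correct-resume steps keep their purpose, and text and table can agree. This reading is possible. But it leaves the reference to the last dose with no work to do, and the text does not state it. Elsewhere Section 6 does count explicitly from suspension of the drug, for example for fatigue in Table 13.

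A second defence is that Section 6.3 leaves final decisions on QTcF discontinuation to the investigator's clinical assessment, with planned deviations agreed beforehand with the PI. That softens the consequence, but does not settle which of the two rules is the guideline.

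A reader might infer more than the documents support:

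- **That treatment ends on detection.** It does not. Electrolyte correction and triplicate ECGs come first, and dosing is barred only if the average stays prolonged. The literal reading removes the time to resolve after that step.
- **That Stratum 2 also fails within course 1,** because no dose is due between day 5 and day 15. That gap is scheduled. A child whose QTcF has normalised by day 15 was not kept off drug by QTcF, and both limits (days 10 and 12) fall before day 15 anyway. Table 14 does not cover the day 5 post-dose ECG.
- **That the adult QTcF rates in Section 2.3.3.3 give the number of children affected.** Those are rates at any time after baseline. The documents give none for an ECG about 10 days after the last dose.
- **That the MTD estimate is distorted.** Only events in the dose-finding period are dose limiting (Section 5.1.3), and discontinuation for QTcF is not itself a listed DLT (Section 5.1.4). A child who completes course 1 with its required monitoring does not become inevaluable by stopping at course 2 day 1. No effect on the MTD is shown.

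**Conclusion.** The inconsistency stands. The text counts from the last dose; Table 14 gives 7 days with no stated start. On the nominal calendar the last dose is 10 days old at three mandatory ECGs (day 1 of courses 2, 3 and 4) in each stratum. Read literally, the text then leaves no resolution window once the triplicate average remains prolonged, contrary to Table 14 and to the resumption step in its own paragraph. The limits differ by 10 days there and by at most 2 days at course 1 day 5, in both cases taking Table 14 to count from the omitted dose.

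The result rests on Monday/Wednesday/Friday dosing with the next course starting on day 29, and on the literal reading of the text. At the Stratum 2 minimum gap of 7 days the clock has not yet expired at the ECG. How many children would meet the conflict cannot be estimated from the documents. This is an ambiguity in a stopping rule that should be corrected, but it does not undermine the dose-finding design.

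**What to change.** Reconcile the stopping sentence in Section 6.3 with the Table 14 row for course 1 day 5 and day 1 of later courses. Name the same event in both places as the start of the 7 days: the last dose, the first abnormal ECG or the first omitted dose. State whether scheduled drug-free days count. Then test the wording on the calendar at day 29 in both strata, across the Stratum 2 rest week after day 5, and at the Stratum 2 minimum gap. Which starting event and which limit are clinically right is for the sponsor to decide.

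The cost is one sentence and one table cell in the next amendment, with no added procedures.
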